**Table 8-2 Part B: Assessment schedule**

## 8.1 Screening

### Screening and re-screening

Re-screening can only occur once a patient has failed screening. It is permissible to re-screen a participant if he/she was potentially exposed to SARS-CoV-2 but has no positive rapid antigen test for SARS-CoV-2 by upper respiratory swab.

#### 8.1.1 Information to be collected on screening failures

Patients who sign an ICF form and are subsequently found to be ineligible prior to randomization will be considered a screen failure. The reason for screen failure should be recorded on the appropriate CRF. The demographic information, informed consent, and Inclusion/Exclusion pages must also be completed for screen failure patients. No other data will be entered into the clinical database for patients who are screen failures, unless the patient experienced a serious adverse event (SAE) during the screening phase (see SAE section for reporting details). If the patient fails to be randomized, the IRT must be notified within 2 days of the screen fail that the patient was not randomized.

Patients who are randomized and fail to start treatment, e.g., patients randomized in error, will be considered an early terminator. The reason for early termination should be recorded on the appropriate CRF.

## 8.2 Patient demographics/other baseline characteristics

Country-specific regulations should be considered for the collection of demographic and baseline characteristics in alignment with CRF.

Patient demographics: date or year of birth, sex, race, predominant ethnicity (if permitted) and relevant medical history/current medical conditions (until date of signature of informed consent) will be recorded in the eCRF. Where possible, the diagnosis and not symptoms should be recorded. Patient race and ethnicity are collected and analyzed to identify variations in safety or efficacy due to these factors as well as to assess the diversity of the study population as required by Health Authorities.

All prescription medications, OTC drugs and significant non-drug therapies prior to the start of the study must be documented. See the protocol [Section 6.2.1](#) Concomitant Therapy for further details on what information must be recorded on the appropriate page of the eCRF.

## 8.3 Efficacy

### 8.3.1 SARS-CoV-2 viral load

The viral load will be measured by means of a nasopharyngeal swab, which will be followed by quantitative reverse transcriptase-polymerase-chain-reaction (RT-PCR) assay at a central laboratory. (Details of the nasopharyngeal swab and the RT-PCR testing will be in the Lab Manual.)

**8.3.2 Medically attended visits related to COVID-19 or death from any cause**  
Hospitalizations ( $\geq$  24 hours of acute care) and emergency room visits related to COVID-19 and deaths from any cause will be recorded on the appropriate CRF page. Admission to an isolation ward for social or logistic reasons is not considered a hospitalization due to worsening of COVID-19 condition.

**8.3.3 Patient reported outcomes**

Patients are being requested to complete 3 Patient Reported Outcomes (PROs) during the study. In case a patient is too ill to complete the PRO assessment, this should be documented in the eCRF.

**8.3.3.1 FDA-recommended 14-symptom questionnaire**

Acute COVID-19 symptoms will be collected up to Day 29 to evaluate the efficacy of ensovibep using a COVID-19 symptoms collection tool containing a 14-symptom questionnaire (Appendix 16.1): feeling hot or feverish, chills or shivering, cough, sore throat, low energy or tiredness, headache, muscle or body aches, shortness of breath, nausea, vomiting, diarrhea, stuffy or runny nose, impaired sense of smell, and impaired sense of taste. This questionnaire will be an electronic clinical outcomes assessments (eCOA) tool completed by the patient.

The 14-symptoms will collectively be referred to as the Food and Drug Administration (FDA) COVID-19 questionnaire ([FDA 2020a](#)).

Also a subset of the most clinically relevant symptoms (feeling hot or feverish, chills or shivering, cough, sore throat, low energy or tiredness, headache, muscle or body aches, shortness of breath) are being analyzed to assess the patients' disease status.

[REDACTED]

**8.3.3.3 SF-36**

Patients will be asked to complete the SF-36 questionnaire on Days 29, 61 and 91.

The Short Form 36 Questionnaire (SF-36) is a widely used measure of health status that can be scored to provide two summary measures of health, the Physical Component Summary (PCS) and the Mental Component Summary (MCS). The SF-36 has been used in other COVID-19 studies ([clinicaltrials.gov](#)). In this study the acute version (1 week recall period) of the SF-36 is being used.

## 8.4 Safety

Safety assessments are specified below with the assessment schedule detailing when each assessment is to be performed.

For details on AE collection and reporting, refer to AE section.

Assessment	Specification
Physical examination	
A complete physical examination (Day 1) will include the examination of general appearance, skin, neck (including thyroid), eyes, ears, nose, throat, lungs, heart, abdomen, back, lymph nodes, extremities, vascular, and neurological. If indicated based on medical history and/or symptoms, rectal, external genitalia, breast, and pelvic exams will be performed.
 
An assessment of general physical appearance will include the examination of general appearance and vital signs (systolic and diastolic blood pressure [BP], heart rate [HR], temperature and pulse oximetry). An assessment of general physical appearance will be performed at all visits starting from Day 3.
 
Information for all physical examinations must be included in the source documentation at the study site. Clinically relevant findings that are present prior to signing informed consent must be recorded on the appropriate CRF that captures medical history. Significant findings made after signing informed consent which meet the definition of an Adverse Event must be recorded as an adverse event.

Vital signs	
Vital signs will include the collection of BP and HR. After the patient has been sitting for 3 minutes, with back supported and both feet placed on the floor, systolic and diastolic BP will be measured using an automated validated device, e.g., OMRON with an appropriately sized cuff. In case the cuff sizes available are not large enough for the patient's arm circumference, a sphygmomanometer with an appropriately sized cuff may be used.
 
If vital signs are out-of-range at screening and/or baseline (see Section 5.2 of the protocol for details), two additional readings can be obtained, so that a total of three consecutive assessments are made, with the patient seated quietly for approximately five minutes preceding each repeat assessment. The last reading must be within the ranges provided in the eligibility criteria in order for the patient to qualify.
 
In case of repeated vital assessments, the eCRF should contain all repeat measurements.

Temperature, respiratory rate and oximetry	Body temperature (in °C), respiratory rate and oxygen saturation (pulse oximeter) will be assessed simultaneous to vital signs.
Height and weight	
Height in centimeters (cm) and body weight (to the nearest 0.1 kilogram [kg] in indoor clothing, but without shoes) will be measured as specified in Table 8-1 and Table 8-2.
 
Body mass index (BMI) will be calculated using the following formula:
 $\text{BMI} = \text{Body weight (kg)} / (\text{Height [m]})^2$

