#### **5.2 Exclusion criteria**

Patients meeting **any** of the following criteria are **not** eligible for inclusion in this study.

1. Requiring hospitalization at time of screening, or at time of study drug administration.
2. Oxygen saturation ( $\text{SpO}_2$ )  $\leq$  93% on room air at sea level or ratio of arterial oxygen partial pressure ( $\text{PaO}_2$  in mmHg) to fractional inspired oxygen ( $\text{FiO}_2$ )  $<$  300, respiratory rate  $\geq$  30 per minute, and heart rate  $\geq$  125 per minute.

**In India**, patients with a respiratory rate  $\geq$  24 per minute or with an oxygen saturation  $\leq$  93% on room air ( $\text{SpO}_2$ ) are not eligible.

3. Known allergies to any of the components used in the formulation of the ensovibep or placebo.
4. Suspected or proven serious, active bacterial, fungal, viral, or other infection (besides SARS-CoV-2) that in the opinion of the investigator could constitute a risk when taking intervention.
5. Any serious concomitant systemic disease, condition or disorder that, in the opinion of the investigator, should preclude participation in this study.\*
6. Any co-morbidity requiring surgery within 7 days of dosing, or that is considered life--threatening within 29 days of dosing.
7. Prior or concurrent use of any medication for treatment of COVID-19, including antiviral agents, convalescent serum, or anti-viral antibodies. Purely symptomatic therapies (e.g., over-the-counter [OTC] cough medications, acetaminophen, and nonsteroidal anti-inflammatory drugs [NSAIDs]) are permitted. Prior vaccination for COVID-19 is permitted.
8. Are concurrently enrolled or were enrolled within the last 30 days or within 5 half-lives (whichever is longer) in any other type of medical research judged not to be scientifically or medically compatible with this study.
9. Are pregnant or breast feeding.
10. Women of child-bearing potential, defined as all women physiologically capable of becoming pregnant, unless they are using highly effective methods of contraception at the time of dosing and for 11 weeks after dosing of study drug. Highly effective contraception methods include:
  - a. Total abstinence (when this is in line with the preferred and usual lifestyle of the patient). Periodic abstinence (i.e., calendar, ovulation, symptothermal, and postovulation methods) and withdrawal are not acceptable methods of contraception.

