### **6.2 Other treatments**

#### **6.2.1 Concomitant therapy**

Ongoing long-term medications should be continued and adjusted as needed for the management of underlying conditions.

Symptomatic therapy to manage COVID-19 symptoms, such as antipyretics, analgesics, or oxygen, is permitted. If local standard of care includes further medications tailored to prevent COVID-19 complications (e.g., anticoagulation), these may be used, with the exception of drugs that are immunomodulators (e.g., interferon, tocilizumab, sarilumab, colchicine), immunosuppressives (e.g., steroids) or antivirals. Patients will be required to get upfront approval from the investigator to start any new prescription, OTC, and herbal medication treatments, with the exception of paracetamol up to 3 g/day, which does not require upfront investigator approval.

All medications, procedures, and significant non-drug therapies (including physical therapy and blood transfusions) administered after the patient was enrolled into the study must be recorded on the appropriate Case Report Forms (CRFs). Prior concomitant therapy defined as all medications taken within 30 days prior to enrollment will also be recorded appropriately in the CRFs.

SARS-CoV-2 vaccinations must not be scheduled up to the Day 29 visit, and if possible, should be postponed to take place after completion of the study (Day 91 visit) as ensovibep may neutralize the effectiveness of the vaccine. If such vaccinations take place prior to the last visit, they need to be documented in the relevant electronic Case Report Form (eCRF).

Each concomitant drug must be individually assessed against all exclusion criteria/prohibited medication. If in doubt, the investigator should contact the medical monitor before randomizing a patient or allowing a new medication to be started.

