**Table 8-1 Part A: Assessment schedule**

Visit Name	S1 [6]	V1		V2	V3	V4	V5	V6	V7	V8	V9
Study Day	-3 to -1	1		3	5	8 ± 2	15 ± 3	22 ± 4	29 ± 5 (EOS) [7]	61 ± 5	EOS[8] / 91 ±7
		pre-dose	post-dose								
STUDY ENTRY AND GENERAL ASSESSMENTS											
Informed consent	(X)	X									
Inclusion/Exclusion criteria	(X)	X									
Demographics	(X)	X									
Complete medical history	(X)	X									
INVESTIGATIONAL PRODUCT											
Ensovibep (MP0420)/Placebo			X								
SAFETY ASSESSMENTS											
Prior/concomitant medication evaluation	Continuous starting after ICF signature, until 3 months after study medication										
Prior/concomitant hospitalization and procedures	Continuous starting after ICF signature, until 3 months after study medication										
AE evaluation	Continuous starting after ICF signature, until 3 months after study medication										
Local tolerability			X								
Physical examination and vital signs [1]	(X)	X									
General physical appearance and vital signs [1]				X	X	X	X		X		X
Body temperature, respiratory rate, oximetry	(X)	X		X	X	X	X		X		X

Visit Name	S1 [6]	V1		V2	V3	V4	V5	V6	V7	V8	V9
Study Day	-3 to -1	1		3	5	8 ± 2	15 ± 3	22 ± 4	29 ± 5 (EOS) [7]	61 ± 5	EOS[8] / 91 ±7
		pre-dose	post-dose								
Weight	(X)	X									X
Height	(X)	X									
Hematology, chemistry and coagulation safety tests		X		X			X		X	X	X
Pregnancy test in WOCBP [2]	(X)	X									X
Birth Control	Continuous until EOS [3]										
	VIROLOGY & SEROLOGY ASSESSMENTS										
Rapid SARS-CoV-2 antigen test	(X)	X									
SARS-CoV-2 sample (quantitative RT-PCR, mutation analysis)		X		X	X	X	X		X		X
PK blood sample		X	XX [4]	X		X	X		X	X	X
Blood sample for serum biomarkers		X		X		X	X		X		X
	CLINICAL ASSESSMENTS										
Symptom score [5]		X		Daily assessment				X	X		

Visit Name	S1 [6]	V1		V2	V3	V4	V5	V6	V7	V8	V9
Study Day	-3 to -1	1		3	5	8 ± 2	15 ± 3	22 ± 4	29 ± 5 (EOS) [7]	61 ± 5	EOS[8] / 91 ±7
		pre-dose	post-dose								

[REDACTED]; AE=adverse event; EOS=end-of-study; FDA=Food and Drug Administration; ICF=informed consent form; PCR=polymerase chain reaction; PK=pharmacokinetics; PRO=patient-reported outcome; RT=reverse transcriptase; S=screening; [REDACTED]; V=visit; WOCBP=women of child-bearing potential.

1. Vital signs consist of systolic and diastolic blood pressure and heart rate.

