2.8.4 Other safety data

2.8.4.1 Vital signs

Vital signs variables include measurements of systolic and diastolic blood pressure, heart rate, body temperature, respiratory rate, oximetry and weight. Clinically notable abnormalities are described in [Section 5.6](#).

Absolute values and change from baseline will be summarized for all vital signs parameter by treatment and scheduled visit.

For selected vital sign parameter, the number and percentage of patients with newly occurring or worsening abnormalities meeting the clinically notable criteria at any time post-baseline, considering all post-baseline data from scheduled, unscheduled and premature discontinuation visits, will be summarized by treatment and parameter.

A listing of all vital signs of patients with notable abnormal vital signs values (with clinically notable abnormalities being flagged) will be generated.

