5.6 Vital signs – definition of clinically notable values

Table 5.6-1 shows the clinical notable criteria for vital signs.

Table 5.6-1 Clinical notable criteria for vital signs

Vital sign	Direction	Patient age at screening	
		< 18 years	≥ 18 years
Systolic blood pressure [mmHg]	High	≥ 95th percentile of the age and height group1	≥ 180 with increase from baseline of ≥20 mmHg
	Low	≤ 5th percentile of the age and height group1	≤ 90 with decrease from baseline of ≥20 mmHg
Diastolic blood pressure [mmHg]	High	≥ 95th percentile of the age and height group1	≥ 105 with increase from baseline of ≥15 mmHg
	Low	≤ 5th percentile of the age and height group1	≤ 50 with decrease from baseline of ≥15 mmHg
	High	≥ 38.4°C	≥ 39.1°C

Vital sign	Direction	Patient age at screening	
		< 18 years	≥ 18 years
Oral body temperature [°C]	Low	≤ 35.0°C	
Pulse rate [bpm] 2	High	1-6 months	> 160
		6-12 months	> 150
		12-18 months	> 140
		18-24 months	> 135
		2-3 years	> 128
		3-4 years	> 123
		4-6 years	> 117
		6-8 years	> 111
		8-12 years	> 103
		12-15 years	> 96
Pulse rate [bpm] 2	Low	≥ 15 years	> 92
		1-6 months	< 120
		6-12 months	< 110
		12-18 months	< 103
		18-24 months	< 98
		2-3 years	< 92
		3-4 years	< 86
		4-6 years	< 81
		6-8 years	< 74
		8-12 years	< 67
Weight	High	increase from baseline ³ of ≥ 2 BMI- for-age percentile categories ⁴	
	Low	decrease from baseline ³ of ≥ 2 BMI- for-age percentile categories ⁴	
Respiratory rate [breath per minute] ^{2,6,7}	High	1-6 months	> 55
		6-12 months	> 50
		12-18 months	> 46
		18-24 months	> 40
		2-3 years	> 34
		3-4 years	> 29
		4-6 years	> 27
		6-8 years	> 24
		8-12 years	> 22
		12-15 years	> 21
		≥ 15 years	> 20
	Low	1-6 months	< 33
		6-12 months	< 30

Vital sign	Direction	Patient age at screening	
		< 18 years	≥ 18 years
12-18 months	<28		
18-24 months	< 25		
2-3 years	< 22		
3-4 years	< 21		
4-6 years	< 20		
6-8 years	< 18		
8-12 years	< 16		
12-15 years	< 15		
≥ 15 years	< 13		

Oxygen saturation Low <=93%

bpm=beats per minute; NHLBI= National Heart, Lung, and Blood Institute;

1 Blood pressure percentiles are calculated for each blood BP record using the method described in Appendix B of the following reference: The Fourth Report on Diagnosis, Evaluation and Treatment of High Blood Pressure in Children and Adolescents. Pediatrics 2004; 114; 555.

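### The SAP's post-baseline SpO2 flag and oximetry summaries ignore supplemental oxygen, so a patient who worsens and is put on oxygen can be counted as not notable

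*Protocol*

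**What the plan says.** **Measurement.** Protocol 8.4, in the row on temperature, respiratory rate and oximetry, states: "Body temperature (in °C), respiratory rate and oxygen saturation (pulse oximeter) will be assessed simultaneous to vital signs". It sets posture, rest and cuff conditions for blood pressure but does not mention the oxygen supply at the time of an oximetry reading. Table 8-1 (Part A) has a row "Body temperature, respiratory rate, oximetry" with entries before dosing on Day 1 and on Days 3, 5, 8, 15, 29 and 91, and no footnote on oxygen.

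**Permitted oxygen.** Protocol 6.2.1: "Symptomatic therapy to manage COVID-19 symptoms, such as antipyretics, analgesics, or oxygen, is permitted". The same section requires medications, procedures and significant non-drug therapies given after enrollment to be recorded on the CRF.

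**Analysis.** SAP 2.8.4.1: "Vital signs variables include measurements of systolic and diastolic blood pressure, heart rate, body temperature, respiratory rate, oximetry and weight". Absolute values and changes from baseline are tabulated by arm and scheduled visit. Patients are also counted by arm if they have "newly occurring or worsening abnormalities meeting the clinically notable criteria at any time post-baseline", using scheduled, unscheduled and premature-discontinuation visits. The criterion in SAP Table 5.6-1 is "Oxygen saturation Low <=93" per cent, and none of the table's footnotes concerns oxygen. The SAP's document history shows that Amendment 1 added this criterion.

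**Eligibility, for comparison.** Exclusion criterion 2 in protocol 5.2 uses the same number with a condition attached: "93% on room air at sea level or ratio of arterial oxygen partial pressure".

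**The concern.** A saturation reading can be interpreted only if one knows what the patient was breathing. The eligibility rule recognizes this, but the post-baseline rule takes over the number without the condition. Oxygen raises the reading and is given because a patient has worsened, so the readings affected are not a random subset.

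Vital signs are a listed secondary safety endpoint in both Parts, and saturation is the vital sign closest to the course of COVID-19. A reader of the notable-value table would take an unflagged patient as one who did not desaturate, and a stable or rising arm mean as reassurance. Under the rule as written, either could reflect treatment with oxygen. What is at stake is how these safety tables are read, not the primary result of either Part.

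**Working it through.** The documents give no figure to reproduce. The check traces a reading from the bedside to the table, then asks what can be said about size.

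**1. Is oxygen status recorded with the reading?** Neither protocol 8.4 nor Table 8-1 asks for it. The eCRF, on which the SAP says it is based, is not among the documents, so a field for it cannot be ruled out. If one exists, the SAP does not use it.

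**2. Does the flag use oxygen status?** No. The rule depends only on the value:

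- Reading of 95% on newly started oxygen: 95 > 93, so not notable.
- Reading of 93% on room air: 93 ≤ 93, so notable.

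**3. Does the change table use it?** No. SAP 2.1.1.5 defines change as post-baseline minus baseline. The lowest whole-number value above the cut-off is 94%. A patient who starts there, worsens, and reads 95% on oxygen contributes 95 − 94 = +1, which appears as an improvement.

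**4. When is a patient missed altogether?** The flag looks at any post-baseline reading. Part A schedules six (Days 3, 5, 8, 15, 29 and 91), and unscheduled ones count too. A patient escapes only if every recorded reading is above 93%. One value at or below 93%, whether before, during or after oxygen, is enough for the flag.

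**5. Is oxygen handled elsewhere in the analysis?**

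- SAP 2.4.2 tabulates COVID-19-related concomitant medications under antivirals, immune-modulating or immunosuppressant drugs, and other. Oxygen has no category of its own.
- Protocol 12.4.5 names ambulatory oxygen in an alternative Part B estimand, which is optional.
- No planned output joins oxygen use to an oximetry reading.

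**6. What can be said about size?** For arm k, let p_k be the true proportion of patients whose room-air saturation falls to 93% or below. Let m_k be the share of those patients whose recorded readings all stay above 93% because of oxygen. Then

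- flagged proportion: f_k = p_k × (1 − m_k)
- ratio between arms: f_1/f_0 = (p_1/p_0) × (1 − m_1)/(1 − m_0)

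If m_1 = m_0 = m, with m below 1, the ratio is unchanged and the difference shrinks by the factor (1 − m). If m differs between arms, the ratio moves up or down according to which arm has the larger m. The documents give neither p_k nor m_k, and m_k could lie anywhere from 0 to 1. The direction for each arm's count is therefore known (f_k ≤ p_k), but the amount is not, and neither is the effect on the ratio.

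**The case against.** The strongest case on the other side has four parts.

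**The flag is wide.** Because any post-baseline reading counts, many patients who go on to oxygen will already have been flagged. This stands. A reader might infer that everyone on oxygen reads as normal, or that the sickest patients are systematically lost. The documents do not support that; they support only that such a patient can be missed.

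**The deterioration is captured elsewhere.** Worsening of COVID-19 beyond its expected course is to be documented as an AE (protocol 10.1.1). Moderate or severe worsening AEs with onset within one week of dosing are AESIs (10.1.4). COVID-19 hospitalization or emergency room visit, or death from any cause, is a Part A secondary endpoint and the Part B primary endpoint. The safety inputs to dose selection in protocol 12.4.2 are ADAs, AESIs, AEs and SAEs, not the oximetry flag. This largely stands and limits the consequence. The cover is partial: the AESI window is one week while oximetry runs to Day 91, and the composite requires a hospital stay of at least 24 hours, an emergency room visit or death, so oxygen given at home need not trigger it.

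**No bias between arms is shown.** A reader might infer that arm differences are necessarily pulled toward zero. With equal masking, only the absolute difference shrinks and the ratio does not move. A change in the ratio needs masking that differs between arms, and the documents contain nothing on that. This stands.

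**Part B is unfinished.** SAP section 1 defers full Part B details to an amendment before its first patient. This stands for the SAP rule in Part B and makes that amendment the natural place for the change. Protocol 8.4, however, applies to both Parts as written.

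**Conclusion.** The point holds in a limited form. The SpO2 criterion and the oximetry summaries take no account of supplemental oxygen, although the protocol permits oxygen and ties the same cut-off to room air at entry. A patient who worsens, starts oxygen and has all recorded readings above 93% can be counted as not notable and can raise the arm's mean saturation. This goes beyond missing detail, because following the written rule produces that result.

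The effect is confined to the oximetry safety tables. Primary endpoints, efficacy analyses and the listed dose-selection inputs are untouched. Its size is unknown, and no rate or arm contrast should be attached to it. The conclusion assumes that some patients receive oxygen at the time of a reading and that the unseen eCRF does not feed oxygen status into these tables. It is worth correcting because the endpoint is a listed one and the change is small.

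**What to change.** **SAP 2.8.4.1 and Table 5.6-1, notable values.** Report by arm the number of patients with either (a) a newly occurring SpO2 of 93% or below, or (b) a post-baseline reading during supplemental oxygen newly started after dosing, taken from the recorded therapy dates. Show (a) and (b) separately as well as combined, so that the measured component remains visible. Restricting (b) to newly started oxygen avoids flagging patients on long-term oxygen for a pre-existing condition.

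**SAP 2.8.4.1, by-visit summaries.** Keep all readings in the main absolute-value and change tables, identify those taken on oxygen, and add a sensitivity summary restricted to readings not on oxygen. On-oxygen readings should not be dropped from the main tables, because that would remove sicker patients on the basis of a post-randomization event.

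**Part B.** Record room air yes/no with each oximetry reading, and write the rule into the SAP amendment already promised. A new field would help Part A little: 381 patients had been treated by 19-Oct-2021, against a target of at least 400.

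**Cost.** One derivation rule and one extra summary in Part A, using data the protocol already requires, and one tick box in Part B. There are three downsides:

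- In Part A, therapy dates only approximate oxygen status at the moment of a reading, more so where SAP 5.1.3 imputes a partial date.
- A course of oxygen begun and ended between two readings does not enter component (b).
- The notable rate will look somewhat higher than under the present rule.

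The change concerns recording and tabulation only. It proposes no clinical threshold and no rule for giving oxygen.
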